3.2 Participants Selection and Enrollment

Patients eligible for initial study screening are those who present with occlusion in the intracranial internal carotid artery (ICA), M1 segment of middle cerebral artery (MCA), intracranial vertebral artery (VA) or basilar artery (BA), presenting beyond 24 hours of symptom onset. All such patients who meet all eligibility criteria as follows and with informed consent will be enrolled in the study.

3.2.1 Inclusion criteria

Patient eligibility for study enrollment is determined based on the following inclusion criteria:

- (1) Age ranging between 18 and 80 years.
- (2) sNA-IAO defined as:
 - ① Time from latest ischemic event (ischemic stroke or TIA) in territory of the qualifying artery to enrollment is beyond 24 hours and within 90 days.
 - ② Occlusion of intracranial ICA, M1 segment of MCA, intracranial VA (with contralateral VA hypoplasia or occlusion) or BA confirmed by computed tomographic angiography (CTA) or digital subtraction angiography (DSA).
- (3) Computed tomographic (CT) or magnetic resonance imaging (MRI) demonstrating Alberta Stroke Program Early CT Score (ASPECTS) ≥ 6 (for anterior circulation) or Posterior Circulation Alberta Stroke Program Early CT Score (pc-ASPECTS) ≥ 6 and pons-midbrain index (PMI) < 3 (for posterior circulation).
- (4) Modified Rankin Scale (mRS) score 0-2 at the time of enrollment.
- (5) Technical feasibility of endovascular recanalization for the qualifying artery evaluated by two experienced interventional neuroradiologists.
- (6) More than one risk factor for atherosclerosis.

(7) Signed informed consent form.

3.2.2 Exclusion criteria

Patients are deemed ineligible for study participation if they meet any of the following exclusion criteria:

- (1) Severe stenosis or occlusion of other arteries, or tandem stenosis proximal to the qualifying artery.
- (2) Intracranial hemorrhagic diseases such as definite Intracranial tumors, any intracranial vascular malformations, hemorrhagic transformation of infarction, spontaneous intracranial hemorrhage (cerebral parenchymal, subarachnoid, subdural, or epidural) within 30 days.
- (3) Non atherosclerotic intracranial artery disease: arterial dissection, moyamoya disease or moyamoya syndrome demonstrated by imaging examination, or a definite medical history of autoimmune vasculitis.
- (4) Evidence of cardioembolic embolism such as atrial fibrillation, prosthetic valve(s), infective endocarditis, mitral stenosis, atrial myxoma, intracardiac clot or vegetation, left ventricular aneurysms, etc.
- (5) Known unstable angina or myocardial infarction within the last 6 months.
- (6) Intolerance or allergic reaction to any treatment-related medication, including aspirin, clopidogrel, heparin, and local or general anesthetics.
- (7) History of life-threatening allergy to contrast dye.
- (8) Severe liver impairment (AST or ALT > 3 times normal, cirrhosis), serum creatinine > 3.0 mg/dl.
- (9) Past history of EC-IC bypass surgery or EVT.
- (10) Major surgery (including open femoral, aortic, or carotid surgery) within previous 30 days or planned in the next 90 days after enrollment.
- (11) Late-stage malignant tumors, cachexia, or other serious diseases and an expected life expectancy of less than 1 year.
- (12) Pregnant, perinatal stage or lactating women.

3.3 Participating Center Eligibility

To minimize selection bias, all participating centers are mandated to systematically enroll consecutive eligible patients according to predefined protocol criteria. To be fully eligible for participation in this study, participating centers selection are required to meet the following minimum criteria:(1) all study centers are required to have performed at least 120 endovascular procedures annually, including at least 40 cases of intracranial artery endovascular procedures; (2) the interventional neuroradiologists at these centers had each performed over 100 endovascular procedures..

3.4 Ethical Issues

All the patients gave written informed consent to participate. The study protocol was approved by the Institutional Ethics Committee of Beijing Tiantan Hospital (approval number: KY2020-114-02), and the respective institutional review boards of all participating centers. Participation in the study did not alter the standard clinical care protocols for enrolled patients.

3.5 Baseline Imaging Evaluation

All participants will have baseline imaging (MRI or CT to rule out ICH and exclude major infarction, and CTA/DSA to confirm an occlusion in the MCA, BA, intracranial ICA or VA), performed as part of institutional standard of care procedures for stroke management. All imaging data of this baseline imaging (including raw data) must be provided to the imaging core laboratory for assessment of collateral

compensation, location of the occlusion and determination of ASPECTS (pc-ASPECTS for posterior circulation), etc.

3.6 Treatments and Study Groups

The technical feasibility of endovascular recanalization for all sNA-IAO patients in this study will be collaboratively evaluated by two experienced interventional neuroradiologists. The decision to select either medical treatment alone or additional ER is made by the patients themselves or their legal representatives. Patients are subsequently divided into two groups according to the treatment they received: the medical group and the endovascular recanalization (ER) group. Patients in ER group will receive endovascular recanalisation procedure (details in procedure part below) plus medical treatment (same as the control group).

3.6.1 Endovascular recanalisation (ER)

For patients presenting with ICA or MCA M1 segment occlusion, ipsilateral cerebral hemodynamic compromise is rigorously evaluated through computed tomography perfusion (CTP) or magnetic resonance perfusion imaging prior to enrollment according to a previous study.³¹ Moreover, the non-contrast and perfusion scans are additionally transferred to the Rapid Processing of Perfusion and Diffusion (RAPID) system, providing analysis of perfusion source images with respect to the DEFUSE 3 criteria¹³.

All patients who are scheduled to undergo ER should receive dual antiplatelet therapy (aspirin 100 mg per day and clopidogrel 75 mg per day) for at least three days before the procedure.

All procedures are performed under general anesthesia by an experienced interventional neuroradiologist. After placement of sheath introducers, heparin is given intravenously to maintain the coagulation time between 200 and 300 s. The 6- or 8- French guiding catheter is located distal to the occluded artery as much as possible. Under the route map, the micro guidewire in combination with a microcatheter and the microcatheter are used to carefully pass through the occluded segment. Angiography with the microcatheter should confirm that the guidewire is in the true lumen. The exchange micro guidewire is then sent into the micro catheter, and the microcatheter is exchanged out. The balloon catheter is advanced smoothly into the occluded segment along the exchange micro guidewire. After the occluded segment is dilated with the balloon, angiography with a guiding catheter is performed. Stents are deployed in cases of residual severe stenosis, vascular dissection and failure to maintain forward flow (according to the judgment of the neuroradiologist to select the stent). If one stent cannot completely cover the lesion, multiple stents can be implanted. Successful recanalization was defined as achieving a modified Thrombolysis in Cerebral Infarction (mTICI)³² grade of 2b or higher, coupled with residual arterial stenosis less than 50% in immediate post-procedural DSA imaging..

After the procedure, if there are no evidence of hemorrhagic complications on the head CT scan, dual antiplatelet therapy is systematically continued. Aspirin 100 mg per day must be used for the entire duration of follow-up, and clopidogrel 75 mg per day (or ticagrelor 90mg twice a day) must be used for 90 days after procedure. After 90 days, the decision to whether to continue clopidogrel therapy will be based on the patient's clinical condition and the investigator's assessment.

3.6.2 Medical treatment

Medical treatment will be identical in both groups. Both groups are prescribed with an medical treatment (includes aspirin 100 mg per day for the entire follow-up and clopidogrel 75mg per day for the first 90 days after enrollment). In instances where clopidogrel pharmacogenetic resistance testing is performed, and the results demonstrate either a loss-of-function CYP2C19 allelic variant or an adenosine diphosphate (ADP)-induced platelet aggregation rate exceeding 40%, alternative antiplatelet agents such as ticagrelor or cilostazol may be strategically implemented as therapeutic substitutes. Atorvastatin will be administered at a dosage of 20 mg to 80 mg per day for one year following enrollment, with the continuation of treatment thereafter contingent upon the patient's condition.

3.7 Risk Factor Management

Risk factor management is based on 2014 American Heart Association/American Stroke Association guidelines³³ for the clinical management of cerebrovascular disorders. Medical management of risk factors consists of normalizing low-density lipoprotein (LDL-C) (target LDL-C: <2.59 mmol/L [100mg/dL]), hypertension (systolic pressure <140 mmHg and a diastolic pressure <90 mmHg; patients with diabetes should be controlled with a blood pressure of <130/80 mmHg), diabetes (hemoglobin A1c [HbA1c] <6.5%), and lifestyle modification(include encompassing smoking cessation, alcohol consumption reduction[up to 2 drinks per day for men and half for women], and targeted weight management interventions [BMI <25 kg/m²], moderate physical exercise [at least 40 minutes per session, 3-4 times per week]).

At each research site, neurologists and study investigators will be principally entrusted with comprehensive management of patients' cerebrovascular risk factors. Should a patient fail to achieve the target goals for risk factor management, a face-to-face clinical consultation with the local neurologist will be required to adjust the patient's medical management.

3.8 Follow-up

All participants will be followed up by the neurologists at 30±7 days, 90±7 days, 1 year ±30 days. The preferred follow-up modality is to implement face-to-face clinical evaluations. At every scheduled follow-up visit, the participants' medication regimens, laboratory tests, risk factor management (as previously outlined), and potential adverse clinical events/outcomes are evaluated by an experienced neurologist and/or neurointerventionalist. When patients are unable to attend on-site clinical follow-ups, a remote telephonic follow-up will be utilized as an alternative method of patient assessment. During the 1-year follow-up period, all patients are required to undergo a neurovascular imaging examination including DSA, CTA or MRA.

For perioperative patients in ER group, a clinical examination including the National Institutes of Health Stroke Scale (NIHSS) and Glasgow Coma Scale (GCS) will be carried out at 24-72 hours after the procedure. Meanwhile, patients will undergo CT to assess the cerebral hemorrhage at 24-72 hours, if possible, supplementary assessment of vessel recanalization status will be conducted through CTA or MRA. At the one-week post-intervention assessment, a clinical evaluation will be conducted, including patients' clinical status, NIHSS score, GCS score, and adverse events.

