Secondary Endpoints	
Secondary outcomes as follows:
 
 • Mortality within 1 year; • Ischemic stroke outside the territory of the qualifying artery within 1 year; • Disabling stroke within 1 year; • TIA in the territory of the qualifying artery within 1 year; • Unplanned revascularization (EC-IC bypass surgery or ER) of the qualifying artery within 1 year; • Myocardial infarction within 1 year; • Composite vascular events within 1 year, including any stroke, myocardial infarction, and unplanned revascularization; • Quality of life assessment (EuroQol-5-Dimensions scale questionnaire) at 1 year; • mRS score at 1 year; • Periprocedural outcomes; • Restenosis or reocclusion (symptomatic or asymptomatic).
Statistical Methods	
 • Categorical variables will be compared between treatment groups using χ^2 or Fisher's exact test. Continuous variables or ordinal variables will be compared between treatment groups using t-test or Wilcoxon-Mann-Whitney test. • The primary and time-to-event secondary outcomes will be compared between the groups using log-rank test. • Kaplan-Meier curves will be used to show the incidence of outcomes over time. • The hazard ratio (HR) and adjusted hazard ratio (aHR) between groups, along with their 95% CIs, will be determined using univariate and multivariate Cox proportional hazards regression models. • Propensity score matching (PSM) will be performed to reduce the possible influence of selection bias and confounders on the outcomes. • A 2-sided P value less than 0.05 is considered to demonstrate a statistically significant difference. • All analyses will be performed with using SAS Version 9.4.

Schedule of assessments

Table 1: Summary of Study Treatment and Study Assessments

Study Requirements	Screening and Baseline	Endovascular recanalisation			Discharge	Follow-up Visits		
		Pre-procedure	Intra-procedure	Post-procedure		30-Day (±7 days)	90-Day (±7 days)	1-Year (±30 days)
Inclusion/Exclusion	X	X						
Informed Consent	X							
Clinical Assessment, Vital Signs, and Physical Exam	X	X			X	X	X	X
Laboratory tests	X					X	X	X
NIHSS (blinded to treatment)	X				X	X		
mRS (blinded to treatment)	X				X	X	X	X
EQ-5D (blinded to treatment)						X	X	X
mTICI assessment		X	X	X				
CT/MRI	X			X			X	X
CTP/PWI	X						X	X
CTA/DSA	X						X	X
Protocol Deviations		X	X	X	X	X	X	X
Medication review and patient compliance survey	X	X	X	X	X	X	X	X

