3.9 Outcomes

3.9.1 Primary outcome

The primary outcome is a composite of any stroke or death within 30 days after enrollment or ischemic stroke in the territory of the qualifying artery from 30 days to 1 year after enrollment.

Ischemic stroke is defined as a new focal neurological deficit of sudden onset persisting for at least 24 hours and confirm by cerebral infarction on CT or MRI. Ischemic stroke are further classified as being either in or out of the territory of the qualifying artery. We regard ischemic stroke either in or out of the territory of the qualifying artery within 30 days after enrollment as a primary outcome, but beyond 30 days through 1 year, only ischemic stroke in the territory of the qualifying artery is considered as a primary outcome. We define symptomatic intracranial hemorrhage (sICH) as parenchymal, intraventricular, or subarachnoid hemorrhage identified on brain MRI or CT, which led to new emergence or worsening of neurological symptoms lasting more than 24 hours or a seizure. Death is categorized as vascular-related or non-vascular-related, and all-cause death is considered a primary outcome within 30 days.

Ischemic stroke and intracranial hemorrhage will be determined by core-lab assessment of imaging, and neurological assessment will be performed at the study site by independent neurologist certified in NIHSS, adjudication of outcomes will be done by an outcome adjudication committee.

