3.13 Blinding

All those involved in the subsequent clinical and imaging assessment of outcomes will be blinded to treatment regime.

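### Protocol 3.8 lets a neurointerventionalist, with the operator not excluded, evaluate events at follow-up visits, which does not fit 3.9.1 and leaves the stated blinding unsupported at that step

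*Protocol*

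**What the plan says.** Protocol 3.8 opens with "All participants will be followed up by the neurologists at 30±7 days, 90±7 days, 1 year ±30 days". It then says that, at each scheduled visit, potential events and outcomes are "evaluated by an experienced neurologist and/or neurointerventionalist". The same sentence covers medication, laboratory results and risk factor control. A telephone call may replace the visit.

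Protocol 3.9.1 says that "neurological assessment will be performed at the study site by independent neurologist certified in NIHSS", that ischemic stroke and intracranial hemorrhage are determined by core-laboratory reading, and that "adjudication of outcomes will be done by an outcome adjudication committee".

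Protocol 3.13 says: "All those involved in the subsequent clinical and imaging assessment of outcomes will be blinded to treatment regime". The SAP repeats this under Follow-up in its section 4. The schedule of assessments (Table 1) marks the NIHSS, mRS and EQ-5D rows as blinded to treatment. Section 3.12 describes a committee of three independent experts, and 3.14 describes masked imaging readers.

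**The concern.** Three statements about who looks for outcomes at the visit do not agree: neurologists, a neurologist and/or a neurointerventionalist, and an independent certified neurologist. The middle one admits the specialty that performs the procedure, in a study where patients or their representatives choose the treatment openly (3.6).

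The visit is where a suspected event enters the record. If the person looking for events knows the treatment, or delivered it, the threshold for noticing a mild deficit, ordering a scan or referring a case could differ between groups. Most exposed are mild ischemic stroke (part of the primary outcome), TIA, mRS, and disabling stroke, which 3.9.2 defines through mRS and NIHSS. Death is not exposed in this way. Because treatment is not randomized, credible outcome assessment is one of the few protections the comparison has left.

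**Working it through.** No arithmetic applies: the documents give no figure for assessor agreement, missed events or unblinding. The check is a comparison of the sections.

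1. **Who may evaluate at the visit.** The and/or wording in 3.8 is satisfied by a neurointerventionalist alone. Section 3.9.1 is satisfied only by an independent neurologist, and the first sentence of 3.8 only by neurologists. A visit run by a neurointerventionalist alone meets one of these three statements and fails the other two.

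2. **Is the operator excluded?** Section 3.6.1 has procedures done by an experienced interventional neuroradiologist. No section bars that person, or the treating team, from follow-up evaluation. Section 3.7 makes site neurologists and study investigators responsible for managing risk factors, so a visit neurologist may also belong to the treating team. Section 3.9.1 does not say what its neurologist is independent of.

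3. **How is the evaluator kept unaware of treatment?** Section 3.13, the SAP and Table 1 assert blinding. None gives a mechanism, such as separating outcome assessment from treatment review or asking patients not to disclose their treatment in person or by telephone.

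4. **Do the later masked steps close the gap?**
   - Ischemic stroke requires a lasting new deficit confirmed by infarction on CT or MRI (3.9.1). CT/MRI is optional at 90 days and 1 year (3.10.4, 3.10.5) and is not listed among the 30-day data (3.10.3). Whether a mild suspected event is scanned can therefore depend on the visit evaluator. The core laboratory reads only scans that were taken.
   - TIA requires that imaging show no new lesion (3.9.2). Masked image reading cannot recover a TIA that the site did not record.
   - The committee reviews complications that are reported to it (3.12). That section calls its members independent but does not describe dossiers with treatment removed. Masking of the committee rests on the general sentence in 3.13.

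   The later steps protect the classification of referred events. They do not protect the decision to refer.

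5. **Direction.** Section 3.8 gives the recanalization group a clinical examination and CT at 24-72 hours and a further evaluation at one week, and describes no counterpart for the medical group. This could raise detection of recanalization-group events within 30 days, when any stroke counts. Visit evaluation by someone with a stake in the procedure could act the other way. The documents give nothing with which to net these off.

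**The case against.** The strongest defense is that 3.8 describes an ordinary clinic visit and speaks only of potential events, while outcome determination sits elsewhere with the certified neurologist, the core laboratory and the committee. Table 1 marks the scales as blinded, and nothing in 3.8 gives mRS scoring to a neurointerventionalist. Section 3.15 adds site training and regular checks. Much of this stands: a referred primary-outcome event is not decided by the visit evaluator, and an infarct on a scan is read by masked readers. It does not cover which events are referred and scanned.

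Medication review is also a weak clue to treatment. Section 3.6.2 makes medical treatment identical in both groups. The antiplatelet course in 3.6.1 is similar, though its 90 days run from the procedure rather than from enrollment. The point does not depend on the drug list.

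A reader might infer three stronger things that the documents do not support:

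- **Operators assess their own patients.** The text allows this by omission but does not say it.
- **The visit evaluation cannot be blinded, so 3.8 and 3.13 flatly contradict each other.** The article in 3.8 is indefinite. A neurointerventionalist who did not treat the patient could in principle be masked, so both sentences could be true. What is missing is any provision that makes them true.
- **The result is biased toward recanalization by some stated amount.** If a share m of recanalization-group events were missed and none in the medical group, the observed risk ratio would be (1 - m) times the true one. The documents give no value for m, so any figure would only return the assumption, and the extra early surveillance could push the other way.

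**Conclusion.** The point holds as an inconsistency and an unsupported claim. Section 3.8 permits a visit evaluator whom its own first sentence and 3.9.1 do not, and no section shows how that evaluator is blinded or kept separate from the operator. The exposure is in ascertainment: suspected strokes and TIAs before they reach the masked steps, and the scales if the same evaluator scores them. Size and direction cannot be determined from the documents.

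The conclusion assumes that the and/or wording means what it ordinarily means, and that no separate site manual supplies the missing exclusion and masking rules. If such a manual exists, the remedy is to cite it and align 3.8 with it. The matter deserves an amendment because blinding is claimed without qualification and the correction is small.

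**What to change.** - In Protocol 3.8, remove the neurointerventionalist from the clause on evaluating events and outcomes. Other visit tasks can stay as they are.
- Assign event screening, mRS and NIHSS, at each visit where they are done, to the independent NIHSS-certified neurologist of 3.9.1. State that independent means neither the operator nor a member of the treating team.
- In 3.12, state that the adjudication committee receives dossiers with treatment information removed where possible.
- If visits are already complete, mask dossiers still awaiting adjudication and report who assessed outcomes in each group. Do not describe the assessment as fully blinded where the operator or treating team took part.

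The cost is a small scheduling burden at sites and some redaction work; no new staff role is needed. Patients may still disclose their treatment to any assessor, so this lowers the risk without removing it.

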3.11.4 Documentation of Adverse Events

All SAEs will be recorded in the case report form (CRF) table. The details of the SAEs, including start time, end time, duration, treatment, outcome, and relationship to the intervention, will also be documented. The frequency of SAEs will be summarized according to the study assignments. All recorded AEs and SAEs will be reported to the investigator. In this study, SAEs primarily refer to disabling strokes, symptomatic intracranial hemorrhages or death within 1 year after enrollment.

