5.1. Primary Outcome

The primary outcome is a composite of any stroke or death within 30 days after enrollment or ischemic stroke in the territory of the qualifying artery from 30 days to 1 year after enrollment.

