7.5 Safety Analyses

Summary tables and data displays will be provided for adverse events as well as serious adverse events (as detailed in the study protocol). Procedure-related complications in the endovascular recanalization group will be analyzed. The Chi-square test or Fisher's exact test will be used to compare the incidence of adverse events and serious adverse events between the treatment groups.

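### Adverse events, and to a lesser extent minor strokes in the first 30 days, are looked for more intensively in the ER group, and the SAP does not allow for this

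*Protocol*

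**What the plan says.** **Common schedule.** Protocol 3.8 states: "All participants will be followed up by the neurologists at 30±7 days, 90±7 days, 1 year ±30 days". Face-to-face visits are preferred. When a patient cannot attend, "a remote telephonic follow-up will be utilized as an alternative method of patient assessment"; this fallback applies to both groups.

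**ER-only schedule.** The same section then adds, for one group: "For perioperative patients in ER group, a clinical examination including the National Institutes of Health Stroke Scale (NIHSS) and Glasgow Coma Scale (GCS"), placed 24-72 hours after the procedure. At that point "patients will undergo CT to assess the cerebral hemorrhage at 24-72 hours". Next, "At the one-week post-intervention assessment, a clinical evaluation will be conducted", covering clinical status, NIHSS, GCS and adverse events. Section 3.10.2 adds perioperative data collection up to day 7.

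**Table 1.** CT/MRI and the primary and secondary outcomes are marked under Post-procedure, a column that exists only for ER. The next CT/MRI mark is at 90 days, and 3.10.4 calls that scan optional. Discharge stands outside the ER block, with clinical assessment, NIHSS, mRS and outcomes marked, so it appears to apply to both groups. NIHSS is marked again at day 30.

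**Use of the data.** The first part of the primary outcome is a "composite of any stroke or death within 30 days after enrollment" (SAP 5.1). SAP 7.5 (Safety Analyses) uses a chi-square or Fisher test to "compare the incidence of adverse events and serious adverse events between the treatment groups". Protocol 3.11.4 says "All SAEs will be recorded in the case report form (CRF) table" and makes no matching statement for non-serious AEs.

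Two details need reconciling. Section 3.8 requires NIHSS at 24-72 hours and one week, but Table 1 has no NIHSS mark under Post-procedure. Table 1 has an NIHSS at day 30, but the list in 3.10.3 omits it.

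**The concern.** Stroke outside the qualifying territory, and hemorrhagic stroke, count towards the primary outcome only in the first 30 days. That is also the window in which the two schedules differ. A mild deficit that lasts more than a day and clears within two weeks would probably be seen at an ER assessment. In a discharged medical patient it would surface only if the patient sought care or recalled it at about day 30. Ischemic stroke also needs CT or MRI confirmation (Protocol 3.9.1), and no scan is scheduled for medical patients between baseline and 90 days.

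Non-serious AEs are more exposed, because they depend most on someone asking and ER patients are asked at an extra visit. A test of AE incidence then partly compares numbers of visits. The SAP has no common ascertainment window and no sensitivity analysis for this.

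**Working it through.** **Is there a figure to reproduce?** No. The documents provided state no sample size, event rate, effect size or detection rate. Every number below is an assumption and shows scale only.

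**1. Scheduled contacts after treatment starts, up to day 30**

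| Contact | ER | Medical |
|---|---|---|
| 24-72 h: NIHSS, GCS, CT | yes | no |
| One week: clinical status, NIHSS, GCS, AEs | yes | no |
| Discharge: clinical assessment, NIHSS, mRS, outcomes (time not fixed) | yes | apparently yes |
| Day 30±7 | yes | yes |

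**2. The 30-day stroke component alone.** Assume a true rate of 5% in both groups, with a share q of medical-group strokes missed. Recorded medical rate = 5% × (1 − q), and ratio = 1/(1 − q).

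- q = 10%: 4.5%, ratio 1.11
- q = 20%: 4.0%, ratio 1.25
- q = 30%: 3.5%, ratio 1.43

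These ratios are not for the quantity that the plan tests, which is the 1-year composite. Adding an assumed 5% of later events, equal in both groups, gives 10/9.5 = 1.05, 10/9.0 = 1.11 and 10/8.5 = 1.18.

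**3. The 1-year composite, allowing for events that cannot be missed.** Let f be the share of primary events in the first 30 days, h the share of those found whatever the schedule (death, severe stroke), and s the medical-group detection of the rest relative to ER. With no true effect:

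ratio ER/medical = 1 / [1 − f(1 − h)(1 − s)]

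| f | h | s | f(1−h)(1−s) | ratio |
|---|---|---|---|---|
| 0.25 | 0.8 | 0.95 | 0.0025 | 1.003 |
| 0.50 | 0.5 | 0.80 | 0.0500 | 1.053 |
| 0.75 | 0.5 | 0.70 | 0.1125 | 1.127 |
| 0.75 | 0 | 0.70 | 0.2250 | 1.290 |

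The range over the grid (f 0.25 to 0.75, h 0 to 0.8, s 0.7 to 0.95) is 1.00 to 1.29. The top value needs every 30-day event to be missable.

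**4. AEs.** The ratio is 1/s: 1.05 at s = 0.95, 1.25 at s = 0.8 and 2.0 at s = 0.5.

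**5. Chance of a false significant excess in ER** (nominal 2.5% in that tail), assuming 200 per group. The normal approximation is Φ[(Δ − 1.96·SE₀)/SE₁], where SE₀ is the pooled and SE₁ the unpooled standard error of the difference.

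Example: true AE risk 20% and s = 0.8, so 20% is recorded against 16%. Δ = 0.04 and both standard errors are 0.0384. (0.04 − 0.0753)/0.0384 = −0.92, and Φ = 0.18.

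| s | AEs, true risk 20% | 1-year composite, true risk 10%, f = h = 0.5 |
|---|---|---|
| 0.9 | 7% | 3.0% |
| 0.8 | 18% | 3.7% |
| 0.7 | 36% | 4.4% |

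Under these assumptions the AE test is badly disturbed and the primary comparison only slightly. The composite column compares two proportions and stands in for the planned log-rank and Cox analyses.

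**The case against.** **Severe events are not missed, and the stroke definition filters out silent findings.** This largely stands for the primary outcome. Death does not depend on visits. An ischemic stroke needs a deficit of at least 24 hours plus infarction on imaging, and sICH must be symptomatic, so an incidental finding on the ER-only CT does not count. Discharge and day-30 NIHSS appear to be common to both groups.

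**Adjudication is independent and assessors are blinded** (Protocol 3.12 to 3.14). This protects the classification of reported events. It cannot recover an event that was never detected.

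**Closer monitoring is inherent in a procedure.** Agreed, and it feeds outcomes that only ER can have. The weakness lies in using those findings in between-group tests without matched ascertainment.

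**Non-serious AEs may never reach the test, since only SAEs are assigned to a CRF table.** This stands in part. Section 3.8 has adverse clinical events evaluated at every scheduled visit, but no document says how non-serious AEs enter the analysis data. Either the planned AE test has no defined source, or it draws on unequal visits.

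**A reader might infer that the planned comparisons are, overall, biased against ER.** The documents do not support that. Protocol 3.6 and SAP 4 group patients by treatment received, the outcome clock starts at enrollment, and Protocol 3.6.1 calls for at least three days of antiplatelet preparation before the procedure. An event after enrollment but before a planned procedure could be counted in the medical group, which would favor ER. The Protocol Synopsis instead groups by treatment selected, and these passages must be reconciled. The opposing effects are of unknown size and cannot be assumed to cancel.

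**Conclusion.** The unequal schedule is plain in the text, and nothing in the SAP offsets it. It may bias the between-group AE test against ER and may slightly inflate ER's 30-day stroke component. With assumed inputs, the spurious 1-year composite ratio is about 1.00 to 1.29, mid case 1.05. For AEs the assumed range is 1.05 to 2.0.

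Three limits apply. The size cannot be derived from the documents. The 1.11 to 1.43 ratios for 30-day stroke should not be read as the effect on the primary outcome. The net direction of all biases in this design is not established, so this point alone does not show that a null or unfavorable result for ER would be an artifact. It also assumes that the Discharge column of Table 1 applies to both groups. If it does not, the imbalance is larger.

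**What to change.** **(a) SAP 7.5 (Safety Analyses).** Limit the between-group test to SAEs, which the protocol describes as mainly disabling stroke, sICH and death and which depend least on visit frequency. Report non-serious AEs descriptively by group, and list separately those found only at ER-specific post-procedure assessments. This removes the most exposed comparison.

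**(b) SAP 7.5 (Primary Efficacy Outcome).** Add a sensitivity analysis with one rule for both groups, for example disabling stroke or death in the first 30 days plus in-territory ischemic stroke from 30 days to 1 year. The definition of disabling stroke in Protocol 3.9.2 includes a one-point mRS rise or a four-point NIHSS rise and gives no assessment time. Disability should therefore be classified from assessments that both groups have. Do not delete events from the ER arm alone: that would remove genuine procedural strokes and hemorrhages and tilt the result towards ER. Report this analysis beside the primary result, not in its place.

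**(c) Only if data collection is still open.** Add a one-week structured symptom and event contact for medical patients, by telephone or in hospital, using existing site neurologists. The match is approximate, because the ER assessment is timed from the procedure and not from enrollment.

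**Cost.** Items (a) and (b) need a few SAP sentences and a way to tell where each AE was found, from event and visit dates or one CRF field. Item (c) costs one short contact per medical patient. The downsides are fewer events in the sensitivity analysis and no formal test for non-serious AEs.
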